## APPENDIX A – REGISTRATION GUIDELINES

The following guidelines have been developed in order to ensure timely registration of your patient.

All patients entered on any CCCWFU trial, whether treatment, companion, or cancer control trial, **must** be linked to the study in EPIC within 24 hours of Informed Consent . Patients **must** be registered prior to the initiation of treatment.

In order to ensure prompt registration of your patient, please:

5. Complete the Eligibility Checklist (attached)
6. Complete the Protocol Registration Form (attached)
7. Alert the WFUHS registrar by phone, *and then* send the signed Informed Consent Form, Eligibility Checklist and Protocol Registration Form to the registrar, either by fax or e-mail.

## CCCWFU # 22215 Eligibility Checklist

Page 1

| Yes                      | No                       | N/A                      | Inclusion Criteria (All responses must be YES in order to enter study)  | Eligibility Confirmation (registrar) |
|--------------------------|--------------------------|--------------------------|---|--------------------------------------|
|  |  |  | Patients must have histologically or cytologically documented relapsed and/or refractory Acute Myeloid Leukemia or granulocytic sarcoma.  |                                      |
|  |  |  | ECOG Performance Status of $\leq 3$ .   |                                      |
|  |  |  | Must be $\geq 18$ years of age.   |                                      |
|  |  |  | Expected survival $>3$ months.  |                                      |
|  |  |  | Women of child-bearing potential (i.e., women who are pre-menopausal or not surgically sterile) must use accepted contraceptive methods (abstinence, intrauterine device [IUD], oral contraceptive or double barrier device), and must have a negative serum or urine pregnancy test within 1 week prior to treatment initiation.
Pregnancy Test: Positive or Negative   |                                      |
|  |  |  | Fertile men must practice effective contraceptive methods during the study period, unless documentation of infertility exists.  |                                      |
|  |  |  | Mentally competent, ability to understand and willingness to sign the informed consent form.  |                                      |
|  |  |  | No radiotherapy, treatment with cytotoxic agents (except CPI-613), treatment with biologic agents or any anti-cancer therapy within the 2 weeks prior to treatment with CPI-613. Hydroxyurea and oral tyrosine kinase inhibitors being used without Grade $\leq 2$ toxicity can be taken until day 1 of therapy. Patients must have fully recovered from the acute, non-hematological, non-infectious toxicities of any prior treatment with cytotoxic drugs, radiotherapy or other anti-cancer modalities (returned to baseline status as noted before most recent treatment). Patients with persisting, non-hematologic, non-infectious toxicities from prior treatment $\leq$ Grade 2 are eligible, but must be documented as such |                                      |
|  |  |  | Laboratory values $\leq 2$ weeks must be:   |                                      |
|  |  |  | 
 
• Adequate hepatic function (aspartate aminotransferase [AST/SGOT] <math>\leq 3</math> x upper normal limit [UNL])
 
  |                                      |
|  |  |  | 
 
• alanine aminotransferase [ALT/SGPT] <math>\leq 3</math> x UNL (<math>\leq 5</math> x UNL if liver metastases present)
 
   |                                      |
|  |  |  | 
 
• bilirubin <math>\leq 1.5</math> x UNL
 
   |                                      |
|  |  |  | 
 
• Adequate renal function (serum creatinine <math>\leq 1.5</math> mg/dL or 133 <math>\mu</math>mol/L).
 
  |                                      |
|  |  |  | 
 
• Left Ventricular Ejection Fraction (by TTE, MUGA or cardiac MRI) sufficient to safely administer mitoxantrone as determined by the treating physician
 
   |                                      |
| Yes                      | No                       | N/A                      | Exclusion Criteria (All responses must be NO in order to enter study)   |                                      |
|  |  |  | Serious medical illness, such as significant cardiac disease (e.g. symptomatic congestive heart failure, unstable angina pectoris, myocardial infarction within the past 6 months, uncontrolled cardiac arrhythmia, pericardial disease or New York Heart Association Class III or IV), or severe debilitating pulmonary disease, that would potentially increase patients' risk for toxicity   |                                      |
|  |  |  | Patients with active central nervous system (CNS) or epidural tumor   |                                      |
|  |  |  | Any active uncontrolled bleeding, and any patients with a bleeding diathesis (e.g., active peptic ulcer disease)  |                                      |

|                          |                          |                          |  |  |
|--------------------------|--------------------------|--------------------------|--|--|
|  |  |  | Pregnant women, or women of child-bearing potential not using reliable means of contraception (because the teratogenic potential of CPI-613 is unknown)  |  |
|  |  |  | Lactating females because the potential of excretion of CPI-613 into breast milk   |  |
|  |  |  | Fertile men unwilling to practice contraceptive methods during the study period  |  |
|  |  |  | Life expectancy less than 3 months   |  |
|  |  |  | Any condition or abnormality which may, in the opinion of the investigator, compromise the safety of patients  |  |
|  |  |  | Unwilling or unable to follow protocol requirements  |  |
|  |  |  | Patients with large and recurrent pleural or peritoneal effusions requiring frequent drainage (e.g. weekly). Patients with any amount of clinically significant pericardial effusion   |  |
|  |  |  | Active heart disease symptomatic coronary artery disease, uncontrolled arrhythmias, or symptomatic congestive heart failure  |  |
|  |  |  | Albumin <2.0 g/dL or <20 g/L   |  |
|  |  |  | Evidence of ongoing, uncontrolled infection.   |  |
|  |  |  | Patients with known HIV infection  |  |
|  |  |  | Patients receiving any other standard or investigational treatment for their cancer, or any other investigational agent for any indication within the past 2 weeks prior to initiation of CPI-613 treatment (the use of Hydrea is allowed) |  |
|  |  |  | Patients who have received immunotherapy of any type within the past 4 weeks prior to initiation of CPI-613 treatment  |  |
|  |  |  | Requirement for immediate palliative treatment of any kind including surgery   |  |
|  |  |  | Patients that have received a chemotherapy regimen with stem cell support in the previous 6 months   |  |

This subject is  eligible /  ineligible for participation in this study.

ORIS Assigned PID: \_\_\_\_\_

Signature of research professional confirming eligibility: \_\_\_\_\_ Date: \_\_\_\_\_

Signature of Treating Physician: \_\_\_\_\_ Date: \_\_\_\_\_

Signature of Principal Investigator\*\*: \_\_\_\_\_ Date: \_\_\_\_\_

\* Examples of source documents include clinic note, pathology report, laboratory results, etc. When listing the source, specifically state which document in the medical record was used to assess eligibility. Also include the date on the document. Example: "Pathology report, 01/01/14" or "Clinic note, 01/01/14"

\*\*Principal Investigator signature can be obtained following registration if needed

**CCCWFU # 22215****Protocol Registration Form****Page 2****DEMOGRAPHICS**

Patient: Last Name: \_\_\_\_\_

First Name: \_\_\_\_\_

MRN: \_\_\_\_\_

DOB (mm/dd/yy): \_\_\_\_\_ / \_\_\_\_\_ / \_\_\_\_\_

SEX: \_\_\_\_\_

 Male Hispanic Female Non-Hispanic

Race (choose all that apply): \_\_\_\_\_

 WHITE       BLACK ASIAN PACIFIC ISLANDER NATIVE AMERICAN

Height: \_\_\_\_\_ inches

Weight: \_\_\_\_\_ lbs. (actual)

Surface Area: \_\_\_\_\_ m^2

Zip Code: \_\_\_\_\_ (required if no MRN)

Primary Diagnosis: \_\_\_\_\_

Date of Diagnosis: \_\_\_\_\_ / \_\_\_\_\_ / \_\_\_\_\_

Dose assignment:  500mg/m^2/day       1,500mg/m^2/day (2,500mg/m^2/day maintenance)**The following are required prior to registration:****CURRENT DISEASE STATUS AT REGISTRATION:** \_\_\_\_\_(1ST relapse, 2ND relapse, 3RD relapse, refractory etc., including allo or auto bone marrow transplant)

| Prior Therapies/
Protocol # if applicable | Start / End Date of
Prior Therapy | Best Response
(CR, PR,
Treatment Failure) | Date of
Best Response | Date of
Relapse | Duration of
Best Response
(in Months) |
|--|--------------------------------------|---|--------------------------|--------------------|---|
| #1 _____                                     | _____ / _____                        | _____   | _____                    | _____              | _____                                       |
| #2 _____                                     | _____ / _____                        | _____   | _____                    | _____              | _____                                       |
| #3 _____                                     | _____ / _____                        | _____   | _____                    | _____              | _____                                       |
| #4 _____                                     | _____ / _____                        | _____   | _____                    | _____              | _____                                       |

COMMENT: \_\_\_\_\_

---

---

---

**PROTOCOL INFORMATION**

Date of Registration: \_\_\_\_\_ / \_\_\_\_\_ / \_\_\_\_\_

MD Name (last) : \_\_\_\_\_

Date protocol treatment starts: \_\_\_\_\_ / \_\_\_\_\_ / \_\_\_\_\_

Informed written consent: \_\_\_\_\_

 YES       NO

(consent must be signed prior to registration)

Date Consent Signed: \_\_\_\_\_ / \_\_\_\_\_ / \_\_\_\_\_

PID # (to be assigned by ORIS): \_\_\_\_\_

*Protocol Registrar can be contact by calling [contact] between 8:30 AM and 4:00 PM, Monday – Friday.*

*Completed Eligibility Checklist and Protocol Registration Form must be hand delivered, faxed or e-mailed to the registrar at [name] or [[contact]](mailto:[contact])*

**CCCWFU # 22215 Eligibility Source Documentation Checklist  
(to be submitted with Protocol Registration Form)**

Page 3

| Source Documents Needed |   | ✓ or
N/A |
|--------------------------------|---|-------------|
| 1                              | Pathology report confirming patient has relapsed and/or refractory Acute Myeloid Leukemia   |             |
| 2                              | Documentation of ECOG Performance Status of $\leq 3$ .  |             |
| 3                              | Most recent H&P documenting patient is $\geq 18$ years of age   |             |
| 4                              | Documentation of expected survival $> 3$ months   |             |
| 5                              | Documentation that WOCBP agree to use accepted contraceptive methods  |             |
| 6                              | Negative serum or urine pregnancy test within 1 week prior to treatment initiation  |             |
| 7                              | Documentation that fertile men agree to practice effective contraceptive methods during the study period  |             |
| 8                              | Copies of all informed consent documents  |             |
| 9                              | Documentation of No radiotherapy, treatment with cytotoxic agents (except CPI-613), treatment with biologic agents or any anti-cancer therapy within the 2 weeks prior to treatment with CPI-613. Patients must have fully recovered from the acute, non-hematological, non-infectious toxicities of any prior treatment with cytotoxic drugs, radiotherapy or other anti-cancer modalities (returned to baseline status as noted before most recent treatment). Patients with persisting, non-hematologic, non-infectious toxicities from prior treatment $\leq$ Grade 2 are eligible, but must be documented as such. |             |
| 10                             | Lab report documenting all initial required lab values  |             |
| 11                             | Documentation that patient has no serious medical illness, such as significant cardiac disease (e.g. symptomatic congestive heart failure, unstable angina pectoris, myocardial infarction within the past 6 months, uncontrolled cardiac arrhythmia, pericardial disease or New York Heart Association Class III or IV), or severe debilitating pulmonary disease, that would potentially increase patients' risk for toxicity   |             |
| 12                             | Documentation that patient does not have an active central nervous system (CNS) or epidural tumor   |             |
| 13                             | Documentation that patient does not have any active uncontrolled bleeding, and any patients with a bleeding diathesis (e.g., active peptic ulcer disease).  |             |
| 14                             | Documentation that patient is not pregnant, lactating or a WOCBP not using reliable means of contraception  |             |
| 15                             | Documentation that patient is not a fertile man unwilling to practice contraceptive methods during the study period   |             |
| 16                             | Documentation that patient does not have a life expectancy less than 3 months.  |             |
| 17                             | Documentation that patient does not have any condition or abnormality which may, in the opinion of the investigator, compromise the safety of patients.   |             |
| 18                             | Documentation that patient is not unwilling or unable to follow protocol requirements.  |             |
| 19                             | Documentation that patient does not have large and recurrent pleural or peritoneal effusions requiring frequent drainage (e.g. weekly). Patients with any amount of clinically significant pericardial effusion.  |             |
| 20                             | Documentation that patient does not have active heart disease including myocardial infarction within previous 6 months, symptomatic coronary artery disease, uncontrolled arrhythmias, or symptomatic congestive heart failure.   |             |
| 21                             | Lab report showing Albumin $\geq 2.0$ g/dL or $\geq 20$ g/L.  |             |

|    |  |  |
|----|--|--|
| 22 | Documentation that patients do not have evidence of ongoing, uncontrolled infection.   |  |
| 23 | Documentation that patients do not have known HIV infection.   |  |
| 24 | Documentation that patient is not receiving any other standard or investigational treatment for their cancer, or any other investigational agent for any indication within the past 2 weeks prior to initiation of CPI-613 treatment (the use of Hydrea is allowed). |  |
| 25 | Documentation that patient has not received immunotherapy of any type within the past 4 weeks prior to initiation of CPI-613 treatment.  |  |
| 26 | Documentation that patient does not Require immediate palliative treatment of any kind including surgery.  |  |
| 27 | Documentation that patient has not received a chemotherapy regimen with stem cell support in the previous 6 months.  |  |
| 28 | Documentation that patient does not have A history of additional risk factors for torsade de pointes (e.g., clinically significant heart failure, hypokalemia, family history of Long QT Syndrome).  |  |

## APPENDIX B – Safety and Toxicity Review Committee SAE Reporting Guidelines

|   |                         |
|---|-------------------------|
| Safety and Toxicity Review Committee (STRC; previously known as CROC) Serious Adverse Event (SAE) Notification SOP | Date: 11/17/2016 |
|---|-------------------------|

### Mandatory STRC SAE Reporting Requirements

This document describes STRC reporting and use of the electronic submission form that is submitted for **unexpected grade 4 and any grade 5 (death during protocol intervention) SAEs on CCCWFU Institutional interventional trial patients**. There are multiple entities that require reporting of SAEs. Each entity has different rules for what is reported, and how it is reported.

Rules used by other entities (Institutional Review Board (IRB), AdEERS, MedWatch, etc.) should NOT be used to evaluate whether an event should be reported to STRC. Only the rules for reporting described in this document should be considered.

As defined in the NCI Data Table 4 reporting guidelines, **CCCWFU Institutional Interventional studies covered by these reporting requirements are defined as: In-house, internally reviewed trials, including those collaborative studies conducted with industry sponsorship in which the center is a primary contributor to the design, implementation, and monitoring of the trial, or participation in a multi-site trial initiated by an institutional investigator at another center.** Institutional trials are almost always authored by a researcher here at CCCWFU. Institutional protocols are labeled NCI Code="I" for Institutional on the protocol screen in ORIS. Cooperative group protocols are **not** considered Institutional, but Research Base trials **are** classified as Institutional.

The STRC is responsible for reviewing SAEs for CCCWFU Institutional Interventional studies, as defined above. STRC currently requires that unexpected grade 4 and all grade 5 SAEs on these trials be reported to the STRC for review. All Clinical Protocol and Data Management (CPDM) staff members assisting a PI in documenting and reporting an SAE that qualifies for STRC reporting are responsible for informing a clinical member of the STRC by phone (or in-person), followed by informing the entire committee via the required email notification.

**THESE REPORTING REQUIREMENTS APPLY TO any faculty or staff member on the study team for a CCCWFU Institutional Interventional trial. Once an event is observed, it is the responsibility of the person who observed the event to be sure that it is reported.**

### What is considered an SAE under this mandatory procedure?

Any **unexpected grade 4** event and **all grade 5 events** (death during protocol intervention) should be reported. These events should be reported if they occur while a patient is on study treatment or if they occur within 30 days of last study treatment (even if patient begins a new treatment during the 30 days). This window of 30 days should be the standard window to be used in all protocols unless a specific scientific rationale is presented to suggest that a shorter window can be used to identify events. In addition, if it is not clear whether the Grade 4 is unexpected it should be reported.

**Table 1: Summary of STRC Reporting Requirements for Institutional Pilot, Phase 1, Phase 2 and Phase 3 Interventional Trials**

STRC reporting may not be appropriate for specific expected adverse events for protocols. In those situations the adverse events that will not require STRC reporting **must be specified in**

|                  | ADVERSE EVENT             |              |                       |              |                       |                       |
|------------------|---------------------------|--------------|-----------------------|--------------|-----------------------|-----------------------|
|                  | Grade 1, Grade 2, Grade 3 |              | Grade 4               |              | Grade 5               |                       |
|                  | Unexpected                | Expected     | Unexpected            | Expected     | Unexpected            | Expected              |
| Unrelated | Not Required              | Not Required | REPORT TO STRC | Not Required | REPORT TO STRC | REPORT TO STRC |
| Unlikely  | Not Required              | Not Required | REPORT TO STRC | Not Required | REPORT TO STRC | REPORT TO STRC |
| Possible  | Not Required              | Not Required | REPORT TO STRC | Not Required | REPORT TO STRC | REPORT TO STRC |
| Probable  | Not Required              | Not Required | REPORT TO STRC | Not Required | REPORT TO STRC | REPORT TO STRC |
| Definite  | Not Required              | Not Required | REPORT TO STRC | Not Required | REPORT TO STRC | REPORT TO STRC |

the text of the approved protocol.

**STRC notification responsibilities of the person handling the reporting/documenting of the SAE:**

1. Make a phone call (or speak in person) to the appropriate clinical member of the STRC as listed below (page if necessary)—see note 2 below
2. Submit the STRC Notification Form WITHIN 24 HOURS of first knowledge of the event. This form is found at either the ORIS main menu page or by going to <http://ccc.wfubmc.edu/oris/strc.aspx>.

This will ensure that all persons that need to be made aware of the event (i.e., study team members and STRC members) will be notified; remember to file a copy of your confirmation. (Form instructions will walk you through the required fields, consult the help page for further instructions.)

3. Ensure that you document that the appropriate person(s) on the STRC has been contacted. This documentation is placed on the STRC Notification form described above.
4. Follow up with/update the clinical member(s) of STRC regarding any new developments or information obtained during the course of the SAE investigation and reporting process.

**Elements to complete the electronic STRC form:**

**Please use 'reply to All' when responding with one of these terms: Definite, Probable, Possible, Unlikely, or Unrelated**

1. Patient ID (ORIS PID)
2. Patient Name
3. Patient MR#
4. CCCWFU(ORIS) Study Number
5. Title
6. PI Name
7. PI Contact Number
8. PI Comments
9. STRC Clinician notified by Phone
10. Notified Date
11. Notified Time
12. STRC Clinician Comments
13. Category [This is the Grade – Either Unexpected Grade 4 or Grade 5 should be entered]
14. Additional Information (IRB Reporting)(after discussion with PI or STRC Clinician)
  - i. Is This Event Related to Protocol Treatment?
  - ii. Is Suspension of the Protocol Needed?
  - iii. Any Changes to Consent or Protocol Needed?
  - iv. Was Nature or Severity of Event Unexpected?
15. Date of the event.
16. Brief description (include brief clinical history relevant to this event, including therapies believed related to event).
17. Date of Last Dose before event
18. Relevant tests/labs.
19. Other Relevant Treatment Information
20. Other Comments/Notes (include regimen of chemo and dates the patient received them if known).
21. Cc (email) (include treating Physician; separate email list with comma",")
22. Your Name
23. Your Email
24. Confirm Your Email

**Definition of Unavailable:**

As a general guideline if the first clinician that is contacted does not respond to the phone call or page within a reasonable amount of time, then initiate contact with their backup. Give the back-up a reasonable amount of time to respond to a phone call or page before contacting another member. This is a general guideline. You must use your best judgment as a clinical research professional given the time of day, severity of the SAE, and other circumstances as to when it is appropriate to contact backup clinicians. If the event occurs near the end of day, then leave messages (voice or email) as appropriate and proceed with submitting your STRC notification form. The important criteria is that you have taken reasonable steps to notify and document that you have initiated some type of contact to one or more of the clinical members of STRC.

**STRC CLINICAN RESPONSIBILITY:**

It is the responsibility of the STRC clinician to review all reported events, evaluate the events as they are reported; and communicate a response to the Investigator, event reporter and the members of STRC. The review will include but not be limited to the information reported; there may be times when additional information is needed in order for an assessment to be made and further communication directly with the investigator may be warranted. STRC reserves the right to agree with the investigator's assessment if STRC does not agree with the investigator. STRC reserves the right to suspend the trial pending further investigation.

Is there any immediate danger or harm that could be present for a future patient based on the information provided in the STRC report – and if so an immediate suspension of enrollment should take place.

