In exploratory analysis we plan to compare both complete response and early mortality (death within 60 days of beginning of treatment) to the observed rates in a historical cohort of subjects (CCCFWFU 22111), both overall and by dose. In the historical cohort the response rate was estimated to be 41%. Using a one-sided chi-square test, a 0.05 significance level, null hypothesis of 41%, and assuming 70% power, we would be able to show significant improvement in response if we are able to achieve a response rate of 56% or higher. Early mortality in the historical cohort was estimated to be 29% at 60 days. We will use a one-sided exact test for a single proportion, a 0.05 significance level, a null hypothesis of 29%, and 70% power. To show a significant decrease in early mortality in this study we would need to observe a 60 day mortality rate of 16.8% or lower.

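### The safety committee's rule for disagreeing with the investigator contradicts itself, and no running count of early deaths by CPI-613 dose is specified

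*Combined protocol and SAP*

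**What the plan says.** **Disagreement.** In Appendix B, the text on the STRC clinician's responsibility reads: "STRC reserves the right to agree with the investigator's assessment if STRC does not agree with the investigator". It continues: "STRC reserves the right to suspend the trial pending further investigation". On scope, the same paragraph says "The review will include but not be limited to the information reported" and that "there may be times when additional information is needed in order for an assessment to be made". A separate question, which leads to immediate suspension of enrollment, asks: "Is there any immediate danger or harm that could be present for a future patient based on the information provided in the STRC report".

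**The form.** Appendix B lists 24 items for the electronic notification and tells those replying to use a five-level attribution term, Definite to Unrelated. Item 14 includes "Is This Event Related to Protocol Treatment" and whether suspension is needed. The items concern one patient and one event. None asks for dose level or cohort, number treated, or deaths so far. The only item specific to dosing is the date of the last dose, although some free-text items could hold more.

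**What is reported, and until when.** Unexpected grade 4 events and all grade 5 events go to STRC whatever their attribution, if they occur on study treatment or within 30 days of the last study treatment.

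**Mortality analysis.** The Analysis Plan in section 10.0 states: "Early mortality in the historical cohort was estimated to be 29% at 60 days". It plans an exploratory, one-sided exact comparison for a decrease, overall and by dose, counting 60 days from the start of treatment. No interim timing is given. Section 5.3 sets 20 patients for each of the 500 and 1,500 mg/m² cohorts.

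**The concern.** Two attributions for one event are foreseeable: the investigator assigns one under section 7.1, and replies to the STRC notice carry another. The only sentence on what then happens cannot be followed as written. A dropped word is the likely cause, but that is inference, and a safety procedure should not rest on it.

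The more consequential matter is what anyone is asked to count. Early death is common in this population, so no single death report is remarkable. An excess at one dose shows only as a count over a denominator, and no one is assigned to keep one. The planned mortality comparison looks for improvement and has no interim look. An excess at one dose could therefore persist until its cohort is full without any step in these documents being designed to show it.

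**Working it through.** **1. The plan's own mortality figure.** Section 10.0 gives p0 = 0.29, a one-sided exact test at 0.05 and 70% power; n = 60 is the sample size used in its other calculations.
- Largest c with P(X ≤ c | 60, 0.29) ≤ 0.05: c = 11, with tail 0.0423 (c = 12 gives 0.078).
- Solving P(X ≤ 11 | 60, p1) = 0.70 gives p1 = 0.1677, which matches the stated 16.8%.

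The figure reproduces. It is a pooled, lower-tail calculation, so it cannot detect an increase.

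**2. What single reports can show in one cohort of 20 at 29%.**
- Expected deaths by day 60: 20 × 0.29 = 5.8.
- P(at least one) = 1 − 0.71^20 = 0.999.
- P(X ≥ 8) = 0.198, P(X ≥ 9) = 0.095, P(X ≥ 10) = 0.0385.

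Death reports are therefore expected in every cohort. Ten of 20 is the smallest final count with an upper tail below 0.05.

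**3. The reporting window against the 60-day endpoint.** In induction cycle 1, CPI-613 runs on days 1 to 5, and the fifth cytarabine dose (12-hourly from day 3) and third mitoxantrone dose fall on day 5. If no further cycle is given, the window closes at day 5 + 30 = day 35. Deaths from about day 36 to day 60 count as early mortality but need not be reported to STRC. Its own reports cannot guarantee a complete 60-day count.

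**4. An illustrative review prompt.** At n = 5, 10, 15 and 20 patients with known day-60 status, take the smallest r with P(X ≥ r | n, 0.29) ≤ 0.05:

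| n | r | P(X ≥ r) at 29% |
|---|---|---|
| 5 | 4 | 0.027 |
| 10 | 6 | 0.040 |
| 15 | 8 | 0.041 |
| 20 | 10 | 0.0385 |

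The probability of a first crossing at each look comes from carrying the binomial distribution of deaths forward five patients at a time and removing paths that have already crossed. For example, at 50% the first look gives P(X ≥ 4 | 5, 0.5) = 6/32 = 0.1875.

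| True 60-day rate | First crossing at 5 / 10 / 15 / 20 | Any look (sum) | Before the last look |
|---|---|---|---|
| 29% | 0.0272 / 0.0274 / 0.0181 / 0.0121 | 0.085 | 0.073 |
| 40% (assumed) | 0.0870 / 0.1059 / 0.0806 / 0.0617 | 0.335 | 0.274 |
| 50% (assumed) | 0.1875 / 0.2197 / 0.1516 / 0.1048 | 0.664 | 0.559 |
| 60% (assumed) | 0.3370 / 0.3195 / 0.1628 / 0.0829 | 0.902 | 0.819 |

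- False prompt in at least one of two independent cohorts at 29%: 1 − (1 − 0.085)² = 0.16.
- Mean number evaluated at the prompt or at cohort end: 14.2 at 50% and 10.9 at 60%.
- These figures ignore the 60-day wait for status. At the planned 10 to 15 patients per year, 60/365 × 10 to 15 gives about 1.6 to 2.5 patients enrolled meanwhile.

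**The case against.** A reader might infer that STRC may only agree with the investigator, that it can neither overrule an attribution nor see excess deaths, and that it is the sole safety review. The documents do not support that reading. The sentence contains no restriction to agreement alone. The sentence after it gives a right to suspend that does not depend on the investigator's view. The review extends beyond the submitted report and allows enquiry to the investigator; only the separate immediate-suspension question is tied to what is "based on the information provided in the STRC report". Every grade 5 event within the window reaches the committee, so it could keep a count of its own. SAEs also go to the drug company and, where applicable, to the FDA. Section 7.3 adds IRB reporting and review of risk by the principal investigator. Section 7.2 places STRC within a Data Safety Monitoring Plan that was not supplied.

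Attribution also matters little here: all five attribution rows of the Appendix B reporting table are identical, so an override would change no STRC report. Dose is not unobtainable either, because patient identifiers link to the dose assignment on the registration form, and free-text items ask about therapies and regimen. Finally, Appendix B is an institution-wide procedure, so its form is the wrong place for a trial-specific tally.

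All of this stands, and it narrows the point. It does not supply a by-dose count with a denominator, and the 30-day window means that a count built only from STRC reports could be incomplete. One further limit is fair: a look at 20 comes after the cohort is fully treated and spares no one in it, so the column before the last look is the better measure of benefit within a cohort.

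**Conclusion.** The point holds in two parts of unequal weight. The disagreement sentence is contradictory and leaves authority over attribution unclear; correcting it is necessary but changes little alone. The substantive gap is the missing by-dose tally of early deaths, with no interim look for an increase. STRC is able to act, but these documents do not arrange for it to receive the count that would tell it when to look.

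A simple prompt would come before the last look with overall probability 27%, 56% or 82% if a cohort's true 60-day rate were 40%, 50% or 60%. These are shares of all cohorts, not of flagged ones. The figures rest on 29% as the reference rate, on independent outcomes within a cohort, and on the three higher rates, which are assumptions. By-dose monitoring under the unsupplied Data Safety Monitoring Plan cannot be ruled out; if it exists, a cross-reference would settle most of this. The change is advisable and cheap.

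**What to change.** (a) Correct the Appendix B sentence so that STRC may disagree with the investigator's assessment, and record both attributions when they differ. If the institution-wide procedure cannot be changed promptly, section 7.2 can state this for the trial.

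(b) In section 7 or 10, rather than on the institutional form, have the statistician keep a running tally for each CPI-613 dose cohort of patients treated and deaths within 60 days of first dose. Take the deaths from the trial's own survival follow-up, so that those after the 30-day window are counted. Send the tally to STRC with each death.

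(c) State a non-binding prompt for review, for example at 4/5, 6/10, 8/15 or 10/20, with its operating characteristics and with every decision left to the committee.

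The cost is one corrected sentence, a short paragraph and a small tally from data the trial already collects. The downside is an occasional review raised by chance: about 1 cohort in 12 at 29%, or about 16% across the two cohorts.
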